## 1.0 Background & Rationale

Advancing age is a primary risk factor for cardiovascular disease (CVD), which remains a pervasive source of death and disability in modern society. Postmenopausal women, in particular, represent a segment of the population that exhibit greater rates of disability and CVD with advancing age compared to men (1). Based on data from the Women’s Health Initiative, wherein estrogen replacement therapy did not exhibit cardioprotective benefits (2), it is essential to consider alternative approaches that may possess therapeutic potential for attenuating CVD risk among postmenopausal women. Indeed, it has become increasingly clear that exercise training is vital to preservation and restoration of physiologic function to achieve optimal health/longevity in many populations (3). However, given that postmenopausal women do not characteristically possess the same responsiveness to exercise training compared to *pre*menopausal women (4) or men (5) – targeted efforts are needed to overcome the limitations of current exercise prescription. Such efforts may attenuate age-related shifts in arterial aging and cardiovascular disease risk by proving to be more effective at reducing vascular oxidative stress/inflammation, as well as, increasing gait/mobility and endothelial function in postmenopausal women.

CVD risk steepens during the menopausal transition (6), likely due to the combined effects of age-related oxidative stress (7), low-grade inflammation (8), and diminishing estrogen (9). Since nitric oxide is implicated in numerous physiological functions, including vasodilation and inhibition of platelet aggregation, boosting nitric oxide bioavailability represents an ideal target to restore physiologic function. From a mechanistic standpoint, age-related oxidative stress reduces nitric oxide bioavailability via the uncoupling of eNOS following the formation of peroxynitrate (10). Historically, the L-arginine-nitric oxide pathway was thought to be the primary source of endogenous nitric oxide production. More recently, though, the nitrate-nitrite-nitric oxide pathway has been identified wherein commensal bacteria on the dorsal surface of the tongue reduce ingested nitrate (e.g. beetroot juice) to nitrite (11). Swallowed nitrite can then be further reduced to stimulate nitric oxide-dependent signaling within the systemic circulation. Functionality of the nitrite-

nitric oxide circuit is best represented by the compelling data in humans showing reduced blood pressure (12) and augmented exercise performance (13).

Since peak plasma concentrations of nitrate and nitrite occur within 1-2 hours and 3-4 hours (following ingestion) (14), respectively, there is a reasonable window of time to perform exercise. By harnessing the reasonable time (2-3 hours), during which, plasma nitrate and nitrite levels are at a maximum, beetroot juice consumption can be planned to coincide to the start of exercise to acutely elicit the following effects in postmenopausal women: 1) greater distance covered during a 6-minute walk; 2) increased endothelial-dependent vasodilation as determined by flow-mediated dilation and; 3) reduced endothelial microparticles (e.g. sVCAM-1, sICAM-1, sE-selectin). Potential findings could inform a larger clinical trial to determine if pre-exercise beetroot supplementation is an efficacious strategy to promote health related effects of exercise training including improved gait/mobility and reduced CVD risk. *To test our hypotheses, we propose a 2-arm randomized controlled pilot to examine the following aims:*

## **2.0 Objective(s)**

### **2.1 Primary Objective**

**Aim 1.** Determine the feasibility of an 8-week (3x/week) exercise training progression (EX) coupled with the consumption of beetroot juice (BR+EX) prior to exercise in postmenopausal women. Prior work supports daily, short-term (21 days) consumption of beetroot juice in men and women aged 62 +/- 1 years, yet this was performed in the absence of exercise training. Research unequivocally supports the utility of exercise training, still in the context of this proposal, feasibility is unknown.

### **2.2 Secondary Objective**

**Aim 2a.** Determine preliminary effects sizes for pre-exercise beetroot juice consumption + exercise training (BR+EX) compared + exercise training only (EX) on distance (feet) covered during a 6-minute walk test. Performance during the 6-minute walk has been shown to accurately estimate peak oxygen uptake (i.e., aerobic fitness) and functional mobility. Consistent with others showing performance benefits of pre-exercise beetroot juice consumption and acute exercise, we anticipate a small to medium effects size in a beneficial direction (i.e., greater positive change) for BR+EX compared to EX.

**Aim 2b.** Determine preliminary effect sizes for BR+EX compared to EX on improvement of endothelial-dependent vasodilation as evidenced by percent increase in flow-mediated dilation. Based on our working premise that beetroot juice may offset the burdens of endothelial dysfunction/activation by increasing nitric oxide bioavailability, coupled with the effects of exercise training, we anticipate a small to medium effect size in a beneficial direction for BR+EX compared to EX.

### **2.3 Tertiary/Exploratory/Correlative Objectives**

**Aim 3.** Determine preliminary effect size for BR+EX compared to EX on reducing soluble endothelial microparticles including, sICAM-1, sVCAM-1, sNCAM, MPO, IFN $\gamma$ , IL-1 $\beta$ , BDNF, TNF- $\alpha$ , and IL-10. Given the link between nitric oxide and regulation of NF- $\kappa$ B, it is reasonable that BR+EX may have synergistic properties that could contribute to

favorable effects on the vascular endothelium. As such, we anticipate a small to medium effect size in a beneficial direction for BR+EX compared to EX.

### **3.0 Outcome Measures/Endpoints**

#### **3.1 Primary Outcome Measures**

Outcomes of interest include recruitment, retention, adherence (i.e., exercise prescription and assessments), perceived exercise difficulty, and adverse event rates. Project success will be based on 83% [20 of 24] of randomized participants completing 8 weeks of exercise training.

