Based on participant responses to the questions, research personnel will determine preliminary eligibility for an on-site visit. If it appears the participant meets the preliminary eligibility, an on-site visit will be scheduled, and a consent form will be mailed / emailed to the participant for their consideration and review. After the study participant has had several days to review the consent form, research personnel will call the participant to answer any further questions regarding the consent form. Participants will be enrolled in small ( $n = 9$ ) cohorts or "waves" to facilitate social support and adherence to the supervised exercise training sessions. We anticipate having 9 waves to successfully reach our target  $n$ . This assumes that each wave will have 4 participants, hence, 4 participants x 9 waves = 36 total participants.

At the on-site screening visit, research personnel will once again cover inclusion/exclusion criteria, study procedures, requirements, and risks. Following written informed consent, participants will have their body weight and standing height measured to determine their body mass index (i.e., 25.0-39.9 kg/m^2). Current prescription drug use will be recorded by having

participants physically bring their prescription labels or medication bottles to the testing site. Additionally, participants will complete a Medical History Questionnaire (see attachments).

Written authorization will be obtained from consented participants to allow research personnel to contact the participant's primary care physician to receive physician's clearance prior to study testing visits. The physician will be asked to provide their assent or dissent for their patient to participate in the exercise testing protocols and supervised group exercise sessions involved with this study. They will have the option to indicate any modifications that may be necessary for the patient to participate safely. The Physician Clearance Form (see attachments) will be faxed to the patient's physician following the screening visit.

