Participants will perform baseline assessments (**Visits 1-2**) prior to randomization. Subsequently, participants will be randomly selected to: 1) control (EX only) or 2) BR+EX. Group allocation will be determined at random using a computer-based number generator in blocks of 2 to ensure equal between-group distribution (i.e.  $n = 2$  Ex only;  $n = 2$  BR+EX). Each number will be kept in a sealed envelope until completion of **Visits 1-2**.

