**6-Minute Walk Test-** Consistent with standard procedures (20), participants will be instructed to walk for six minutes around an indoor, closed course during **Visits 2 and 3**. A chest-strap heart rate monitor will be worn to measure changes in heart rate before and after walking, and a triaxial accelerometer will be used to examine signal profile associated with movement complexity (i.e. movement accelerations) and estimates of energy expenditure (kilocalories). The accelerometer will be worn on the non-dominant hip and fastened with an elastic belt. Subjects will additionally be asked to identify their level of perceived exertion on a continuous visual analog scale (“no exertion” to “maximal exertion”) after the test.

**Supervised Exercise Training (CrossFit, Bloomington)-** Participants randomized to exercise training will perform combined aerobic and resistance workouts in a group setting with a cohort of approximately 4 women also enrolled in the study. There is a chance that participants will complete the exercise training sessions with other individuals who are not enrolled in the study. This will be outlined in the Informed Consent Statement provided to participants.

Full participation in the exercise training intervention is defined as attending 3 sessions per week for a total of 8 weeks (24 sessions total). The sessions will be supervised by a certified fitness professional who will make adjustments to the workouts based on individual needs/abilities. Each one-hour session will consist of a warm-up, instruction of the workout, a workout of combined aerobic and resistance training exercises, and cool-down. Intensity of the exercise sessions will be progressed gradually from weeks 1 to 8 and monitored by having participants identify their rating of perceived difficulty for each session using a discrete visual analog scale (0-10). The intensity of exercise sessions will also be monitored through continuous heart rate assessment (Actiheart) during week 2, week 4, and week 6 of training.

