Additionally, events that do not meet prompt reporting criteria, but are still considered reportable will be communicated to the IU IRB at the time of the next study renewal. These events would include:

1. Local adverse events, which were not previously promptly reported and occurred at a greater frequency and/or severity than was initially anticipated. In relationship to the relevant study procedures, this may include:
  - a. A greater frequency and/or severity of symptoms related to beetroot juice ingestion (e.g. gastrointestinal distress), muscle soreness during the walking and/or muscle strength tests, discomfort or bruising with needlestick blood draws.
  - b. Injuries or medical conditions that do not require hospitalization and are not considered medically important (e.g. twisted ankle, sore muscles/joints, pulled muscle).
  - c. Enrollment of a greater number of subjects that does not exceed the total study-wide enrollment number (i.e. 37-50 subjects enrolled).
  - d. Conduct of research procedures by individuals who are not listed as approved personnel on the study protocol.
  - e. Implementation of minor wording changes to study documents.

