### **10.0 Data Safety Monitoring**

[name] (Department of Kinesiology) will work with [name] (Department of Kinesiology) to oversee aspects of data management and safety monitoring for the current investigation, including: data quality, subject recruitment, accrual, retention, outcome and adverse event data. Both are independent of the PI and funding source. [name] is not directly affiliated with the study but will be responsible for performing periodic inspection of data quality and random assessments of participant recruitment, retention, adherence, and adverse events.

[name] and [name] will hold in-person meetings once every 3 months to address items related to data quality. However, [name] will perform periodic assessments at random to examine participant recruitment, retention, adherence, and adverse events.

As a safety precaution, potential side effects of acute beetroot juice ingestion will be determined for each participant during visit 1. Stopping criteria will be instituted (i.e., participant withdrawn) if a participant exhibits, during a 3-hr period, either a drop of >20 mm Hg in systolic blood pressure or a value of 12% in blood methemoglobin (determined via CO-oximeter).

Statistical analyses will be conducted on validated statistical software (e.g. SPSS, SigmaPlot) and results will be reported through traditional scientific outlets such as peer-reviewed journals and presentations. All analyses will be done without the use of any identifying features to individuals enrolled (e.g. use of ID codes, saving electronic data using ID codes rather than subject name).

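### The success threshold of 20 of 24 randomised is not reconciled with the 36-participant target, and a pooled exercise-completion rule does not by itself answer Aim 1

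*Combined protocol and SAP*

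**What the plan says.** **Success rule.** Section 3.1 of the combined protocol and SAP lists recruitment, retention, adherence, perceived difficulty and adverse event rates as primary outcomes. It then sets one threshold: "Project success will be based on 83% [20 of 24] of randomized participants completing 8 weeks of exercise training". It explains adherence by reference to the exercise prescription and the assessments.

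**Numbers planned.** Section 6.0 says "We anticipate having 9 waves to successfully reach our target" and gives the sum as "4 participants x 9 waves = 36 total participants". Allocation is by computer-generated numbers "in blocks of 2 to ensure equal between-group distribution", illustrated as two EX and two BR+EX. Section 7.0 describes training "in a group setting with a cohort of approximately 4 women also enrolled in the study". Section 9.0 lists "37-50 subjects enrolled" as an over-enrolment event to report at renewal, which fits a plan of 36.

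**Steps before allocation.** Consent is followed by BMI and medication checks and by physician "clearance prior to study testing visits" (Section 6.0). Under Section 10.0, "potential side effects of acute beetroot juice ingestion will be determined for each participant during visit 1", with withdrawal criteria. Randomisation comes after Visits 1-2.

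**Aim 1 and its analysis.** Section 2.1 asks whether the 8-week training is feasible when combined with beetroot juice. Section 7.0 provides exhaled nitric oxide checks of juice compliance in weeks 3 and 6. Section 12.0 plans descriptive statistics and rates for Aim 1.

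**The concern.** A feasibility threshold works only if its denominator is known before the data are seen. Twenty-four appears elsewhere only as a number of sessions or bottles, never as a participant total. The participant target in Section 6.0 is 36. A reader cannot tell whether the trial should randomise 24 or 36, and so cannot tell whether 20 or 30 completers are needed.

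The second issue is what the threshold measures. The open question in Aim 1 is the combination, which only BR+EX participants receive during training. Pooling lets good completion in EX offset poor completion in BR+EX, and juice compliance has no direct part in the rule. A pass could therefore be carried into a larger trial as evidence that the combination is feasible when the BR+EX data do not show it.

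**Working it through.** **1. The plan's own figures.** 20/24 = 0.833, which agrees with 83%, and 0.83 x 24 = 19.92, rounded up to 20. 4 x 9 = 36. Each figure is right by itself; the gap lies between them.

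**2. What would link 36 to 24.** A loss of (36 - 24)/36 = 33% before randomisation, leaving 24/9 = 2.7 randomised per wave. No section states such a loss. The two-plus-two illustration and training groups of about 4 suggest 4 randomised per wave, or 36 in all. That is an inference: the protocol does not say it.

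**3. The rule at 36 randomised.** 0.83 x 36 = 29.88, rounded up to 30, and 30/36 = 83.3%. By contrast 20/36 = 55.6%.

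**4. The lowest BR+EX result that still passes.** With equal arms and every EX participant completing:
- 24 randomised: 20 - 12 = 8, so BR+EX 8/12 = 67%.
- 36 randomised: 30 - 18 = 12, so BR+EX 12/18 = 67%.

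Exact (Clopper-Pearson) 95% limits are the 0.025 quantile of Beta(x, n - x + 1) and the 0.975 quantile of Beta(x + 1, n - x). They give 35-90% for 8/12 and 41-87% for 12/18.

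**5. How often a pass would hide a BR+EX result below 83%.** Below 83% means fewer than 10 of 12, or fewer than 15 of 18. With independent binomial arms of size m, pooled requirement r and BR+EX mark g:

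P = sum over b = 0 to g - 1 of P[Bin(m, pB) = b] x P[Bin(m, pE) >= r - b]

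with (m, r, g) = (12, 20, 10) or (18, 30, 15). The documents give no completion rates by arm, so the true rates are assumed.

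| Assumed EX / BR+EX | 24 randomised | 36 randomised |
|---|---|---|
| 85% / 85% | 0.09 | 0.10 |
| 90% / 75% | 0.22 | 0.27 |
| 95% / 67% | 0.32 | 0.35 |

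The first row is sampling variation alone. The other rows assume gaps of 15 and 28 percentage points.

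**The case against.** **Enrolled is not randomised.** Section 3.1 counts randomised participants, while Sections 6.0 and 9.0 count enrolled or total participants. Several checks and the Visit 1 juice challenge fall between consent and allocation, so 36 enrolled and 24 randomised is possible. This stands. A reader might infer that the protocol plans to randomise 36 and that 24 is simply wrong. The documents do not go that far, and the cues are mixed. Section 6.0 also describes cohorts of 9. A block of 2 in two arms gives one per arm, not two. The heart-rate paragraph in Section 7.0 speaks of 3 participants, one per treatment group, in a trial with two arms. What remains is that the step from 36 to 24 is stated nowhere.

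**One rule, not two.** A reader might also infer that the count and the percentage are rival rules. At an assumed 70% true completion with 36 randomised, at least 20 completers has probability 0.98 and at least 30 has 0.05. That contrast requires detaching 20 from its denominator of 24. Section 3.1 reads most naturally as a proportion with a worked fraction, so the contrast is not a property of the rule as written.

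**Pooling is legitimate and juice is not ignored.** Pooled completion is a fair part of feasibility, and Section 3.1 sets 83% for all randomised participants, not for each arm. Juice problems can lower the count indirectly through intolerance or withdrawal, and compliance is measured. Section 12.0 also mentions between-group comparison of descriptive data, which may or may not extend beyond baseline. All of this stands. It limits the point to what a pooled pass can be said to show.

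**Conclusion.** The point holds as a failure to reconcile, not as a demonstrated error in the 83%. Either the bracketed count is out of date or the randomised target is missing, and the documents cannot settle which. If 36 are randomised, the same proportion needs 10 more completers than the bracket shows.

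The pooled rule can be met with BR+EX at 67%. How likely a pass is with BR+EX below 83% depends entirely on the assumed rates: about 0.1 if the arms are truly equal, and about a third if BR+EX is much worse. This does not make the pooled rule invalid. It means that a pass, reported alone, supports a statement about the exercise programme and not about the combination in Aim 1.

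Severity is minor to should-fix: this is the only numeric threshold for the primary aim, but the trial is a pilot and the repair is mostly wording.

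**What to change.** (a) **Denominator.** In Sections 3.1 and 6.0, state the enrolment target and the randomised target separately, with any loss expected between them. Make 83% of all randomised participants the governing rule and match the bracketed count to it: 20/24 if 24 are randomised, 30/36 if 36. The Section 9.0 figures can stay as enrolment limits.

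(b) **Reporting for Aim 1.** Keep the pooled rule. In Section 12.0, add completion for EX and BR+EX separately with exact 95% CIs. Summarise the week 3 and 6 juice checks descriptively for BR+EX only: EX receives no juice during training, no exhaled nitric oxide cutoff is given, and no log of servings is described. Let a pooled pass support a statement about the exercise programme only, unless the BR+EX estimate and interval are presented with it as the Aim 1 result.

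(c) **Completion.** Reconcile what completing 8 weeks means. Section 3.1 does not define it. Section 7.0 defines full participation as 24 sessions but requires 17 of 24 for follow-up assessments, and Sections 7.0 and 11.0 add withdrawal rules for missed sessions. Which rule applies is for the sponsor to decide.

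**Cost.** Wording in three sections and tables mostly from data already collected. Per-arm intervals are wide (10/12: 52-98%; 15/18: 59-96%), and feasibility of BR+EX becomes somewhat harder to claim. No per-arm pass/fail gate is proposed, because an arm truly at 83% would miss 10/12 with probability 0.33 and 15/18 with probability 0.37. If the randomised target is 36, the move from 20/24 to 30/36 leaves the chance of passing unchanged only near 85% true completion (0.71 for both). At 80% it falls from 0.46 to 0.40, and at 70% from 0.111 to 0.054.

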#### **3.2 Secondary Outcome Measures**

**2a.** The distance (feet) covered during a 6-minute walk test at baseline prior to the intervention and following BR+EX is the main secondary outcome of interest. To confirm the relationship of the functional 6-minute walk test to aerobic fitness, measures of oxygen consumption (ml/kg/min or L/min), heart rate (bpm), and blood pressure (mm Hg) will be taken during constant speed walking at a typical walking pace prior to the 6-minute walk test. Additionally, functional mobility will be assessed by analyzing triaxial movement patterns from an accelerometer worn on the non-dominant hip during the 6-minute walk test.

The BR+EX intervention will be considered successful in the event that there is a statistically significant increase in 6-minute walk distance (feet) along with a decrease in oxygen consumption (ml/kg/min or L/min), decrease in exercising heart rate (bpm), improvement in heart rate recovery following exercise (post exercise heart rate – heart rate 1 min, 2 min after exercise (bpm)), decrease in exercising blood pressure (mm Hg), decrease in post-exercise blood pressure (mm Hg), and/or improvement in gait function (i.e. preferred walking speed, center of mass characteristics) from baseline to post-intervention above any improvement seen in EX.

**2b.** Percent changes in brachial artery diameter (%), cutaneous vascular conductance (%), and pulse wave velocity (m/s) at baseline prior to the intervention and following BR+EX are secondary outcomes of interest, representing changes in endothelial dependent vasodilation. A non-invasive technique of flow mediated dilation of the brachial artery using ultrasound imaging will be used to assess the percent change in vessel diameter following occlusion. A local heating protocol using non-invasive Laser Doppler flowmetry in conjunction with blood pressure measurements will be used to obtain measures of red blood cell (RBC) flux and mean arterial pressure (MAP) to calculate cutaneous vascular conductance (RBC flux/ MAP). The velocity of the pulse wave traveling from the carotid to femoral artery will be assessed non-invasively using tonometry.

A statistically significant increase in the percent change in brachial artery diameter (%), cutaneous vascular conductance (%), and/or a decrease in pulse wave velocity (m/s) in BR+EX above any improvement observed in EX from baseline to post-intervention will be considered a successful outcome.

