### 3.3 Tertiary/Exploratory/Correlative Outcome Measures

Tertiary outcome measures of interest include plasma concentrations of sICAM-1, s-VCAM-1, sNCAM, MPO, IFN $\gamma$ , IL-1 $\beta$ , BDNF, TNF- $\alpha$ , and IL-10 obtained from a venous blood sample taken at baseline and post-intervention.

Statistically significant decreases in endothelial microparticle concentrations from baseline to post-intervention in BR+EX that are above any decrease observed in EX will be considered a successful outcome.

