### **12.0 Statistical Considerations**

Rather than confirm efficacy, this proposal addresses elements of feasibility such that we intend to generate preliminary effect sizes for a larger-scale investigation. Descriptive statistics and calculation of rates (e.g., recruitment, retention, adherence, and adverse event) will be used for study aim 1. Between-group differences in descriptive data along with aims 2(a,b) and 3 will be evaluated using an unpaired t-test. Effect size calculations will be performed with Cohen's  $d$  to qualify substantive differences: small (0.2), medium (0.5), and large (0.8). Potential covariates of interest include age, body mass, body fat percentage, and/or markers of inflammation. Non-normally distributed data will be log-transformed. Two-tailed parametric correlations (Pearson) will be performed and based on consequent results, multiple linear regression will be used to examine changes in inflammation, endothelial function, distance in 6-minute walk test, leg strength, and resting blood pressure/arterial stiffness.

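### Sections 3.2 and 3.3 declare success on statistical significance although Section 12 disclaims confirming efficacy, and the rules as worded leave the 6-minute-walk and marker verdicts uninterpretable

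*Combined protocol and SAP*

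**What the plan says.** Section 12.0 states the purpose: "Rather than confirm efficacy, this proposal addresses elements of feasibility such that we intend to generate preliminary effect sizes for a larger-scale investigation". Sections 2.2 and 2.3 word Aims 2a, 2b and 3 the same way and anticipate a small to medium benefit for each.

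The outcome sections nevertheless attach efficacy verdicts.
- **2a (Section 3.2):** "The BR+EX intervention will be considered successful in the event that there is a statistically significant increase in 6-minute walk distance (feet"), together with a list of further changes joined by and/or, over the intervention period and beyond any gain in EX.
- **2b (Section 3.2):** a significant increase in brachial dilation, "cutaneous vascular conductance (%), and/or a decrease in pulse wave velocity (m/s) in BR+EX above any improvement observed in EX".
- **Markers (Section 3.3):** "Statistically significant decreases in endothelial microparticle concentrations from baseline to post-intervention in BR+EX that are above any decrease observed in EX". The list opens "Tertiary outcome measures of interest include plasma concentrations of sICAM-1, s-VCAM-1, sNCAM, MPO" and runs to nine analytes. How many must fall is not stated.

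Section 12.0 gives the test: "Between-group differences in descriptive data along with aims 2(a,b) and 3 will be evaluated using an unpaired t-test". It uses Cohen's d "to qualify substantive differences: small (0.2), medium (0.5), and large (0.8"). It states no alpha, no multiplicity rule, no confidence interval and no standardising SD for d.

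Section 3.1 has a separate feasibility criterion: "Project success will be based on 83% [20 of 24] of randomized participants completing 8 weeks of exercise training".

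**The concern.** A pilot that disclaims confirming efficacy should not carry rules that pronounce an intervention successful or not on a p-value. Three things could follow.

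- At pilot size, a real effect of the anticipated magnitude could be reported as a failure.
- Where the rule does not say which comparison or how many endpoints count, an inert supplement could be reported as a success, with the reading chosen after the data are seen.
- The effect sizes, which are what the larger study needs, would be passed on with a small, medium or large label and no stated uncertainty.

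**Working it through.** The documents give no power or alpha for these aims, so there is no plan figure to reproduce. The one success figure they do give checks: 20/24 = 83.3%.

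**Inputs from the documents**
- Unpaired t-test; d = 0.2 small, 0.5 medium (Section 12.0).
- Small to medium effect anticipated (Sections 2.2 and 2.3).
- 24 randomized and 20 completing (Section 3.1); 36 in total (Section 6.0); ceiling of 50 (Section 9.0).
- Equal allocation (Section 6.0), giving 12, 10, 18 and 25 per arm, with completers assumed to split evenly.

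**Assumptions:** two-sided alpha 0.05; where several endpoints are combined, the same d on each and a common correlation of 0 to 0.8.

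**1. 2a as a between-arm test, d on the SD of the analysed variable.** Favourable power is P(T > t(0.975, 2n-2)), where T is noncentral t with 2n-2 degrees of freedom and noncentrality d x sqrt(n/2). The smallest observed d that reaches significance is t(0.975, 2n-2) x sqrt(2/n); at n = 12 this is 2.074 x 0.408 = 0.85.

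| Per arm | Power, d=0.2 | Power, d=0.5 | Smallest significant d |
|---|---|---|---|
| 10 | 6.2% | 18.4% | 0.94 |
| 12 | 6.8% | 21.5% | 0.85 |
| 18 | 8.4% | 30.8% | 0.68 |
| 25 | 10.3% | 41.0% | 0.57 |

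These are upper limits for 2a, because the accompanying conditions can only lower them. One-sided testing at 0.05 raises the d=0.5 figures to 28%, 32%, 43% and 54%.

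**2. 2a with d on the raw-score SD and change scores tested.** With equal SDs at both visits and baseline to follow-up correlation r, the effective d is d / sqrt(2(1-r)). At d=0.5 and r=0.8 this is 0.5/0.632 = 0.79.
- d=0.5, r=0.8 / 0.9: power 46% / 75% at 12 per arm, and 64% / 90% at 18.
- Power at d=0.5 passes 50% at r of about 0.82 (12 per arm) or 0.72 (18 per arm).
- d=0.2: at or below 26% for up to 18 per arm and r up to 0.9.

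**3. 2a read as within-arm significance plus a numerically larger gain than EX.** Simulated at 12 per arm, assuming exercise alone shifts the mean change by 0.5 to 0.8 SD of change. Success with an inert supplement is 28% to 45%; at d=0.2 it is 51-66%, and at d=0.5 it is 82-88%.

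**4. Section 3.3, nine markers, between-arm tests, 12 per arm.** With independent markers and no effect, any-of-nine gives 1 - 0.975^9 = 20.4%. Simulation at other correlations:

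| Correlation | Any-of-nine, no effect | Any-of-nine, d=0.5 | All-of-nine, d=0.5 |
|---|---|---|---|
| 0 | 20% | 89% | about 0% |
| 0.5 | 14% | 63% | 1% |
| 0.8 | 8% | 46% | 6% |

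**5. 2b, any one of three.** With no effect, 1 - 0.975^3 = 7.3% if independent, falling to about 5% at correlation 0.8.

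**6. Precision of what is handed on.** An observed d of 0.35 at 12 per arm has t = 0.35 x sqrt(6) = 0.857. Inverting the noncentral t gives a 95% interval of -0.46 to 1.15, from below zero to beyond large.

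**The case against.** The best defence is that these are secondary and tertiary labels in a pilot. Section 3.1 ties project success to completion alone, and no section makes a decision about the larger study depend on the Section 3.2 or 3.3 verdicts. That stands, and it limits the consequence to a reported verdict.

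A reader might infer more than the documents support in four places.

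- **That 2a is bound to miss a medium effect.** It is not. The standardising SD and the baseline correlation are not given, and step 2 shows power above one half at d=0.5 under plausible combinations. Section 12 also lists possible covariates and a regression of walk-distance changes, and adjustment could raise power further. What survives is the small end of the range, where power stays low on every between-arm reading examined at up to 18 per arm.
- **That the rule is certainly the between-arm test.** Section 12 favours this, but the Section 3.2 wording also admits a within-arm reading, and the error then runs the other way (step 3).
- **That 2b turns on an unstated any-or-all choice.** It does not: and/or ordinarily lets one endpoint suffice, and false success is then only about 5-7%. Brachial dilation is described in Section 3.2 but appears in neither the Section 7.0 procedures nor the Section 8.0 calendar. If it is not collected, two endpoints remain and the figure is at most 1 - 0.975^2 = 4.9%. 2b is a minor matter.
- **That any-of-nine always means a false success in every five to seven trials.** That holds only for correlations of 0 to 0.5; at 0.8 the rate is about 8%. The plural in Section 3.3 also sits awkwardly with a single-marker trigger.

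**Conclusion.** The conflict between Section 12 and the success sentences in Sections 3.2 and 3.3 is plain on the text and should be resolved.

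For 2a, the rule would miss the anticipated effect in most trials (favourable power 6-18% at 10 per arm, 7-22% at 12, 8-31% at 18). This rests on three conditions: the between-arm test, two-sided 0.05, and d on the SD of the analysed variable. Changing the SD or the reading changes the answer, and the plan fixes neither.

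For 3.3, the missing count of markers moves the verdict from about 8-20% false success to almost certain failure (about 6% success or less at d=0.5 and 12 per arm).

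The sample-size discrepancy between Sections 3.1 and 6.0 does not alter these conclusions. The point merits correction but does not threaten the feasibility aim.

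**What to change.** Delete the significance-based success sentences in Section 3.2 (2a and 2b) and Section 3.3, so that the completion criterion in Section 3.1 is the only success rule.

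Add to Section 12.0: For Aims 2a, 2b and 3, the between-arm difference in change from baseline and Cohen's d, with the standardising SD named, will each be reported with a 95% confidence interval; no outcome will be declared successful on a p-value.

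If a success rule is kept, state that it is the between-arm test and give its alpha. State also how many of the nine markers Section 3.3 requires, and which of the and/or items in 2a must be met.

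The cost is wording in three sections, with no new data, visits or participants. What is given up is a yes/no efficacy verdict that Section 12 already disclaims.
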